PRODUCT: V501/V503	PROTOCOL/AMENDMENT VERSION NO.: V503-088-01-v1
REVOPS ID NO: NIS009722	CORE DRC APPROVAL DATE: 18JUL2024
EPIDEMIOLOGY NO.(PE STUDIES ONLY): EP08039.017	

PAES INFORMATION

Title	Population-based retrospective nested case-control study evaluating effectiveness of GARDASIL TM /GARDASIL TM 9 against adult-onset recurrent respiratory papillomatosis (AoRRP) in Sweden, Denmark, and Norway.
Protocol Version identifier	V503-088-01-v1
Date of last version of protocol	Aug 31, 2022
HMA-EMA Catalogue of Real- World Data:	EUPAS48452
Active substance:	Each dose of Quadrivalent Human Papillomavirus Recombinant Vaccine (GARDASIL®, G4) contains 20 μg HPV 6 L1 VLP, 40 μg HPV 11 L1 VLP, 40 μg HPV 16 L1 VLP, and 20 μg HPV 18 L1 VLP, along with 225 μg of alum. Each dose of Nonavalent Human Papillomavirus Recombinant Vaccine (GARDASIL®9, G9) contains 30 μg HPV 6 L1 VLP, 40 μg HPV 11 L1 VLP, 60μg HPV 16 L1 VLP, 40 μg HPV 18 L1 VLP, 20 μg HPV 31 L1 VLP, 20 μg HPV 33 L1 VLP, 20 μg HPV 45 L1 VLP, 20 μg HPV 52 L1 VLP, and 20 μg HPV 58 L1
	VLP, along with 500 μg of alum.
Medicinal product(s):	G4: Quadrivalent Human Papillomavirus Recombinant Vaccine
	G9: Nonavalent Human Papillomavirus Recombinant Vaccine
Joint PAES	No

1

PRODUCT: V501/V503	PROTOCOL/AMENDMENT VERSION NO.: V503-088-01-v1
REVOPS ID NO: NIS009722	CORE DRC APPROVAL DATE: 18JUL2024
EPIDEMIOLOGY NO.(PE STUDIES ONLY): EP08039.017	

Research question and objectives	Primary Objective:
	To assess if the odds of AoRRP are lower among females fully vaccinated with GARDASIL/GARDASIL9 before the age of 17 years versus those unvaccinated.
	Secondary Objectives:
	1) To assess annual age-standardized incidence rates of AoRRP (ages 15-29 years) among males and females.
	2) To assess annual age-standardized incidence rates of juvenile-onset recurrent respiratory papillomatosis (JoRRP) (ages 0-14 years) among males and females.
Country(-ies) of study	Sweden, Denmark, and Norway
Author(s)	PPD Principal Scientist, Merck Sharp & Dohme Corp., a subsidiary of Merck & Co., Inc., [name] PPD Associate Principal Scientist, Merck Sharp & Dohme Corp., a subsidiary of Merck & Co., Inc., [name] PPD Principal Investigator, Dept of Laboratory Medicine, Division of Pathology, Karolinska Institutet, [name], PPD Principal Investigator Dept of Research, Cancer Registry of Norway [name] PPD

PASS	Post-Authorization Safety Study
PIN	Personal Identification Number
PQC	Product Quality Complaint
RR	Relative Risk
RRP	Recurrent Respiratory Papillomatosis
SAP	Statistical Analysis Plan
SCR	Swedish Cancer Register
SD	Standard Deviation
SNOMED	Systemized Nomenclature of Medicine
SOP	Standard Operating Procedure
SYSVAK	Norwegian Immunization Registry
SQI	Significant Quality Issue

PRODUCT: V501/V503	PROTOCOL/AMENDMENT VERSION NO.: V503-088-01-v1
REVOPS ID NO: NIS009722	CORE DRC APPROVAL DATE: 18JUL2024
EPIDEMIOLOGY NO.(PE STUDIES ONLY): EP08039.017	

2 ABSTRACT

Title	Population-based retrospective nested case-control study evaluating effectiveness of GARDASIL TM / GARDASIL TM 9 against adult-onset recurrent respiratory papillomatosis (AoRRP) in Sweden, Denmark, and Norway.
Protocol Number / Version	V503-088-01-v1
Date	18Jul2024
Author	PPD
Rationale & Background	Recurrent respiratory papillomatosis (RRP) is a medical condition where HPV types 6 and 11 cause wart-like growths in the larynx. The condition is rarely fatal but associated with high morbidity. Current treatment only offers temporary symptomatic relief. There is an expectation that HPV vaccination targeting types 6 and 11 will reduce incidence of RRP. To date, no study has evaluated the effectiveness of HPV vaccination against AoRRP. Due to the low incidence of AoRRP, a randomized controlled trial to evaluate the efficacy of HPV vaccination against RRP would be prohibitively large and complex. The comprehensive national registry systems of Sweden, Denmark, and Norway afford the opportunity to evaluate the effectiveness of GARDASIL/GARDASIL 9 in lowering the risk of AoRRP in the female population with minimal biases due to completeness and representativeness of the data.

PRODUCT: V501/V503	PROTOCOL/AMENDMENT VERSION NO.: V503-088-01-v1
REVOPS ID NO: NIS009722	CORE DRC APPROVAL DATE: 18JUL2024
EPIDEMIOLOGY NO.(PE STUDIES ONLY): EP08039.017	

Research Question(s) &	Primary Objective:
Objective(s)	To assess if the odds of AoRRP are lower among females fully vaccinated with GARDASIL/GARDASIL 9 before the age of 17 years versus those unvaccinated.
	The study success criterion requires demonstration that the odds ratio comparing unvaccinated to vaccinated females be \geq 3.0 and the lower bound of 95% CI be \geq 1.33.
	Secondary Objectives:
	1) To assess annual age-standardized incidence rates of AoRRP (ages 15-29 years) among males and females.
	2) To assess annual age-standardized incidence rates of JoRRP (ages 0-14 years) among males and females.
	Exploratory Objectives:
	To assess factors associated with risk of AoRRP.
Study Design	Population-based nested case-control study (primary objective);
	Population-based ecological study (secondary objectives)
Population	Primary objective:
	All females 15-29 years of age after 2006 and eligible for HPV vaccination at <17 years of age, i.e., birth cohorts 1990 and later.
	Secondary objective:
	All individuals (males and females) 0-29 years of age between the following calendar years and birth cohorts:
	• Sweden: 2000 – 2021 (birth cohort, 1971 – 2021)
	• Denmark: 1997 – 2022 (birth cohort, 1968 – 2022)
	• Norway: 2008 – 2022 (birth cohort, 1979 – 2022)
	Exploratory objective:
	Same population as the primary objective.

PRODUCT: V501/V503	PROTOCOL/AMENDMENT VERSION NO.: V503-088-01-v1
REVOPS ID NO: NIS009722	CORE DRC APPROVAL DATE: 18JUL2024
EPIDEMIOLOGY NO.(PE STUDIES ONLY): EP08039.017	

Variables	Exposure definition:
	Full receipt of GARDASIL/GARDASIL 9 vaccination regimen for effectiveness evaluation (2 or 3 doses according to age at vaccination).
	Outcome definitions:
	• First diagnosis of AoRRP (females only) identified from national registries for primary analysis.
	• First diagnosis of JoRRP and AoRRP (males and females) from national registries for incidence rates assessment in secondary analyses.
	Covariates:
	Vaccination age, history of external genital warts (EGW), and sociodemographic variables (education level, income).
Data Sources	Nordic population, patient, and vaccine registries.
Study Size	Sample size
	Primary objective (nested case-control study):
	Cases: <50 AoRRP cases in each country.
	Controls: 10 controls per case will be selected.
	Secondary objectives (ecological study): Descriptive/no power calculation. Entire age eligible population during specified calendar years in Sweden, Denmark, and Norway will be eligible.
Data Analysis	Power calculation for primary objective:
	A total of 60 AoRRP cases from Sweden, Denmark, and Norway will provide the study with approximately 80% power to detect an odds ratio equal to 3.0 with a corresponding lower bound of 95% CI of odds ratio equal to 1.33.
	Primary analysis:
	Conditional logistic regression for estimation of ORs and corresponding 95% CIs. In the main analysis, only vaccination before 17 years of age will be considered as exposure.

PRODUCT: V501/V503	PROTOCOL/AMENDMENT VERSION NO.: V503-088-01-v1
REVOPS ID NO: NIS009722	CORE DRC APPROVAL DATE: 18JUL2024
EPIDEMIOLOGY NO.(PE STUDIES ONLY): EP08039.017	

Milestones	Planned Date
Start of data collection:	26Oct2021 (Actual)
End of data collection:	3Q2024
Final report of study results:	1Q2025

PRODUCT: V501/V503	PROTOCOL/AMENDMENT VERSION NO.: V503-088-01-v1
REVOPS ID NO: NIS009722	CORE DRC APPROVAL DATE: 18JUL2024
EPIDEMIOLOGY NO.(PE STUDIES ONLY): EP08039.017	

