7.8 Study Size

Power analysis for the primary objective (nested case-control study):

Estimated power to evaluate the primary objective is presented in this section. Our primary hypothesis is that AoRRP risk is lower among females fully vaccinated with Gardasil before age 17 years versus those who are never vaccinated before case/control selection. This could be also stated as AoRRP risk is higher among females unvaccinated for HPV compared to those who are vaccinated at age < 17 years. The statistical criterion for success requires that the odds ratio (OR) for this comparison be \geq 3.0 and lower bound of the 95% confidence interval (CI) for the OR be \geq 1.33. In observational studies, high effect estimates are considered important to demonstrate strong associations and to assess causality. Conventionally, odds ratios of <2 are considered to represent weaker associations by epidemiologists, as it may not be possible to judge whether the association can be entirely accounted for by bias [39]. A threshold of 3.0 is therefore proposed to establish the effectiveness of Gardasil vaccination in preventing RRP. Prior Nordic registry studies reported Gardasil effectiveness against genital warts ranging from 38%-88% (equivalent to ORs of 1.6-8.3) and cervical intraepithelial neoplasia grade 2+ ranging from 22%-82% (equivalent to ORs of 1.3-4.0) with higher effect among females vaccinated at younger age.

Based on prior available information (i.e., publicly available gross statistics on ICD codes for otorhinolaryngological diseases), the Sponsor's power calculations (summarized below) at first suggested that it may be possible to test this hypothesis in Sweden alone. However, at the time when this protocol was initially drafted, the exact number of cases were not known and therefore it was noted that a decision to conduct the analysis would be made once data were received from the registries, i.e., when the exact number of cases occurring in relevant birth cohorts was confirmed.

Estimated number of AoRRP cases:

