Study power was estimated according to varying number of AoRRP cases (from 40 to 80), effect size (odds ratio from 3.0 to 4.0), and weighted female vaccination coverage (20 to 30%) with constant alpha-level of 0.05, control/case ratio of 10 in the age range of focus (Table 1). To detect a true OR of 3.0 with an overall vaccination coverage of 25% in all three countries combined, approximately 60 AoRRP cases would be needed to achieve a power of at least 80%, which would not be possible by including data from individual countries alone. Precision was also considered by specifying that the analyses for the primary objective be powered to detect an OR of at least 3.0, with a lower bound for the confidence interval of at least 1.33, which is equivalent to lower bound of 95% CI of vaccine effectiveness >25%. Preliminary estimates of vaccination coverage among females in the proposed age group (<17 years) obtained from public registries are ~20% for Sweden, ~50% for Denmark, and ~25% for Norway, and is expected to be at least 25% overall. By pooling data from Sweden, Denmark, and Norway for the primary analysis, the estimated combined number of AoRRP cases occurring after Gardasil introduction in these three countries (birth cohorts 1990+) is expected to be above 60 with >80% power assuming true odds ratio of 3.0 and 25% vaccination coverage (Table 2). Previously, individual level registry data were successfully pooled across multiple Nordic countries (Denmark, Finland, and Sweden) in a case-control study evaluating risk of male breast cancer in association with finasteride use [40].

In Sweden, Denmark and Norway, the attribution of HPV types contributing to HPV-related diseases (including RRP) is similar, and the median age of sexual debut among females is also similar (~16 years) [28]. As expected, prior studies in these countries have reported similar vaccine effectiveness against HPV-related diseases, including against cervical cancer in Sweden and Denmark, i.e., 88% and 86% effectiveness among females who were vaccinated at <17 years of age, respectively [20] [21]. Also, in a very recent Norwegian analysis focusing on Gardasil vaccine effectiveness against CIN2+, investigators reported 82% effectiveness among females vaccinated <17 years of age (lower compared with estimates above but expected given the higher attribution of HPV types other than 16 and 18 in cervical precancer versus cancer) [41].

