PRODUCT: V501/V503	PROTOCOL/AMENDMENT VERSION NO.: V503-088-01-v1
REVOPS ID NO: NIS009722	CORE DRC APPROVAL DATE: 18JUL2024
EPIDEMIOLOGY NO.(PE STUDIES ONLY): EP08039.017	

Table 2 Power estimates according to varying number of cases of AoRRP (from 40 to 80), effect size (odds ratio from 3.0 to 4.0), and vaccination coverage (20-30%), with constant alpha-level of 0.05, lower bound of 95% confidence interval >1.33, control/case ratio of 10.

True	%	Number of AoRRP cases								
effect size	Vaccine coverage	40	45	50	55	60	65	70	75	80
OR = 3	20	0.40	0.46	0.48	0.52	0.57	0.60	0.61	0.65	0.68
	25	0.67	0.71	0.76	0.76	0.80	0.82	0.82	0.85	0.87
	30	0.85	0.87	0.88	0.91	0.92	0.93	0.94	0.95	0.96
OR = 3.5	20	0.48	0.55	0.60	0.65	0.68	0.71	0.75	0.75	0.80
	25	0.77	0.79	0.83	0.86	0.87	0.90	0.92	0.93	0.93
	30	0.91	0.93	0.94	0.95	0.96	0.97	0.98	0.98	0.98
OR = 4	20	0.57	0.63	0.68	0.74	0.76	0.79	0.83	0.85	0.87
	25	0.84	0.86	0.89	0.92	0.93	0.94	0.95	0.96	0.97
	30	0.95	0.96	0.97	0.98	0.98	0.99	0.99	0.99	0.99

Regarding evaluation of Gardasil effectiveness against JoRRP, the Sponsor has similarly proposed including additional data from Denmark and Norway due to study power limitations in Sweden alone.

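### The stated 80% power at a true odds ratio of 3.0 with 60 cases holds neither for the protocol's two-part success rule nor for its 1.33 lower limit alone; both give about 45%.

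*Protocol*

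**What the plan says.** The rule has two parts and is stated twice. In the abstract: "The study success criterion requires demonstration that the odds ratio comparing unvaccinated to vaccinated females be" at least 3.0, with a lower 95% limit of at least 1.33. Section 7.8 gives the same pair, opening with "The statistical criterion for success requires that the odds ratio (OR) for this comparison be" at least 3.0, and then defends the first part: "A threshold of 3.0 is therefore proposed to establish the effectiveness of Gardasil vaccination in preventing RRP".

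Power is stated in four places: the abstract (60 cases "will provide the study with approximately 80% power to detect an odds ratio equal to 3.0"), the text of Section 7.8, Table 2 and Annex 1. The planning assumption in Section 7.8 is put as "To detect a true OR of 3.0 with an overall vaccination coverage of 25% in all three countries combined", for which about 60 cases are said to give at least 80%. The caption of Table 2 names as its condition a "lower bound of 95% confidence interval >1.33, control/case ratio of 10" and makes no mention of the estimate having to reach 3.0. For a true odds ratio of 3 and 25% coverage the table shows 0.80 at 60 cases and 0.87 at 80; at 30% coverage and 80 cases it shows 0.96.

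**The concern.** The value taken as the truth for planning equals the value that the estimate must reach. An estimator centred on the true log odds ratio falls below it about half the time, however many cases there are. A power figure of 80% or more at a true odds ratio of 3.0 therefore cannot be the probability of meeting the two-part rule.

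That raises a second question: whether 80% is at least right for the one condition named in the table caption, the lower limit of 1.33.

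Insufficient power in Sweden alone is the protocol's stated reason for pooling three countries, and 60 cases is its stated requirement. If the figure is wrong, the chance of meeting the criterion is misstated wherever power is cited.

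**Working it through.** **Inputs, from the abstract and Section 7.8.** 60 cases, 10 controls per case (600 controls), 25% coverage among controls, true odds ratio 3.0, two-sided 95% interval, lower-limit threshold 1.33, point-estimate threshold 3.0.

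**Expected counts.** The odds of vaccination in controls are 0.25/0.75 = 1/3, so in cases 1/9, a probability of 0.10. The expected numbers vaccinated are 6 of 60 cases and 150 of 600 controls.

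**What the lower limit demands.** SE of the log odds ratio = sqrt(1/6 + 1/54 + 1/150 + 1/450) = 0.441. At this SE a lower limit of 1.33 needs an estimate of 1.33 × exp(1.96 × 0.441) ≈ 3.15, already above 3.0. With controls at their expected 150/450:

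- 6 vaccinated cases: OR = (54/6)/3 = 3.00; lower limit = 3.00/exp(1.96 × 0.441) = 1.26. Fails 1.33.
- 5 vaccinated cases: OR = (55/5)/3 = 3.67; SE 0.477; lower limit 1.44. Passes.
- 8 vaccinated cases: OR = (52/8)/3 = 2.17; SE 0.391; lower limit 1.006. Passes a limit of 1, not 1.33.

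The normal approximation gives P(lower limit ≥ 1.33) = Φ[(ln 3 − ln 1.33)/0.441 − 1.96] = 0.455.

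**Attempt to reproduce Table 2.** Exact enumeration of two binomials with a Wald interval, true odds ratio 3.0:

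| Cases | Coverage | Table 2 | Lower limit ≥ 1.33 | Estimate ≥ 3.0 | Both | Lower limit > 1 |
|---|---|---|---|---|---|---|
| 60 | 20% | 0.57 | 0.324 | 0.528 | 0.324 | 0.670 |
| 60 | 25% | 0.80 | 0.454 | 0.525 | 0.453 | 0.798 |
| 60 | 30% | 0.92 | 0.555 | 0.519 | 0.517 | 0.874 |
| 80 | 25% | 0.87 | 0.611 | 0.522 | 0.522 | 0.913 |
| 80 | 30% | 0.96 | 0.707 | 0.519 | 0.519 | 0.955 |
| 100 | 25% | – | 0.727 | 0.520 | 0.520 | 0.965 |
| 120 | 25% | – | 0.815 | 0.518 | 0.518 | 0.986 |
| 140 | 25% | – | 0.877 | 0.517 | 0.517 | 0.995 |

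Simulation of matched 1:10 sets analysed by conditional logistic regression (20,000 runs) agrees at 60 cases and 25% coverage: 0.448 for the 1.33 limit, 0.449 for both conditions, 0.799 for a limit above 1. The headline 0.80 thus coincides with a test against an odds ratio of 1. That reading does not reproduce the table as a whole: it misses the 60-case cells at 20% and 30% coverage and the 80-case cell at 25%. Reading coverage as the prevalence among cases gives 0.73, 0.79 and 0.82 for the 1.33 limit at 60 cases, against the table's 0.57, 0.80 and 0.92. No variant tried reproduced all cells.

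**Which condition limits power.** At 60 cases and 25% coverage the point-estimate condition is almost redundant (0.454 against 0.453). From about 80 cases at 25% coverage, or 60 at 30%, it is the binding one and joint power stays at about 0.52. It tends to 0.50: at 500 cases it is 0.51.

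**Unequal coverage.** Section 7.8 gives about 20% for Sweden, 50% for Denmark and 25% for Norway. The split of cases is an assumption. Simulated results, in that country order:

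- 46/7/7 cases: limit 0.44, both 0.44.
- 20/20/20 cases: limit 0.58, both 0.52.
- 46/45/45 cases: limit 0.93, both 0.51.

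**Joint power at larger true effects, 25% coverage.** With 60 cases: 0.58-0.59 at 3.5, 0.68-0.69 at 4, 0.80-0.82 at 5, 0.86-0.90 at 6. The upper figure counts samples with no vaccinated case as successes. With 100 cases: 0.805 at 4.

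**Separate conversion check.** Odds ratio = 1/(1 − effectiveness). 22% gives 1.28, 38% gives 1.61 and 88% gives 8.33, all as printed. 82% gives 1/0.18 = 5.56, whereas Section 7.8 prints "ranging from 22%-82% (equivalent to ORs of 1.3-4.0) with higher effect"; 4.0 corresponds to 75%.

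**The case against.** The best defence is that 3.0 is a design alternative and 1.33 a precision target. One sentence in Section 7.8, on powering the analysis to detect at least 3.0 with a lower bound of at least 1.33, can be read that way. The reading does not survive the two places that make 3.0 part of the success criterion, nor the sentence that proposes it as a threshold for establishing effectiveness. It would not save the figure either, since the 1.33 limit alone gives 45%.

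A second defence is that 3.0 is a floor rather than the expected effect. This has force. Section 7.8 cites 82-88% effectiveness for vaccination before age 17, or odds ratios of about 5.6 to 8.3, and expects more than 60 cases with coverage of at least 25%. At a true value of 5 the joint rule reaches about 80% with 60 cases. Against that, those figures concern cervical outcomes, and Section 7.13 warns that herd protection may lower the estimates here. The power claims are also made at 3.0.

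Three stronger inferences are tempting and should not be drawn:

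- That leaving out the point-estimate condition explains the gap between 80% and 45%. At 60 cases and 25% coverage it changes power by only 0.001; the lower limit does the work.
- That the study will miss its criterion about half the time. That applies only if the true odds ratio is exactly 3.0.
- That a missed criterion would be taken as evidence against the vaccine. Nothing in the protocol bears on this.

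Stopping Table 2 at 4.0 is not an error in itself, and the 82% conversion feeds no power input.

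**Conclusion.** The power statement is wrong as written. At its own inputs, the probability of success is about 45%, not 80%, under either the two-part rule or the 1.33 limit alone. With more cases or higher coverage, joint power at a true odds ratio of exactly 3.0 levels off at about 50-52%, so the cells of 0.87 and 0.96 cannot be probabilities of success.

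The figures rest on equal coverage across matched sets, a Wald interval and no covariate adjustment. Exact and conditional-logistic calculations agree to within 0.01 where both were run. Under the country mixes examined, joint power ranged from 0.44 to 0.52. How Table 2 was produced cannot be determined from the protocol.

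The 82%-to-4.0 conversion is a separate, minor error.

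**What to change.** Recompute Table 2 for the joint rule and restate power in the abstract, Section 7.8 and Annex 1. At 25% coverage and 10 controls per case: about 45% at 3.0, 69% at 4 and 80-82% at 5 with 60 cases; about 80% at 4 with 100 cases. Add rows for true odds ratios above 4.0, where the joint rule reaches 80% with 60 cases, and state the calculation method so that the table can be reproduced.

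The sponsor may instead make a lower limit of at least 1.33 the sole test and report descriptively whether the estimate reaches 3.0. Power must still be restated: about 45% at 60 cases, with 80% at a true odds ratio of 3.0 and 25% coverage needing about 120 cases (0.798 at 115, 0.815 at 120). The protocol puts each country below 50 cases (Sweden 46), so such a total is possible but not assured.

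In Section 7.8, correct the odds ratio for 82% effectiveness from 4.0 to 5.6.

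The cost is one recalculation and rewording in four places, with no new data. The stated power becomes less favourable.

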3 AMENDMENTS AND UPDATES

Update no	Date	Section of Study Protocol	Update	Reason	CORE DRC Approval Date	CORE DRC Version No
1	13Mar22	7.1, 7.6.2, 7.10	Case and control matching criteria	Regulatory agency feedback	25Apr22	2.0
		7.6.3, 7.10	Covariates	Regulatory agency feedback	25Apr22	2.0
		7.8, 7.10	Sample size and power	Regulatory agency feedback	25Apr22	2.0
2	31Aug22	PAES Information	Changed the quantity of alum for GARDASIL®9 vaccine to 500 µg.	Due to an error in the previous version of the protocol.	n/a	2.1
		7.6.2, 7.6.3	Changed the case definition for the secondary objective and the covariate definition to match the case definition for the primary objective (≥ 1 instead of >1 hospitalization or outpatient record).	To correct the case definition of the secondary objective and covariate.	n/a	2.1
3	21Jun23	4	Milestone dates updated.	Due to data collection period extension.	27Jul23	3.0
		7.1, 7.2, Annex 2 (Tables 2, 3, and 5; Figures 2 and 3)	Data collection period extended to 2021.	Inclusion of most recent data available from registries.	27Jul23	3.0
		7.8	Inserted description of strategy to pool data with other Nordic countries to improve power/precision.	Pre-specify analysis approach.	27Jul23	3.0

PRODUCT: V501/V503	PROTOCOL/AMENDMENT VERSION NO.: V503-088-01-v1
REVOPS ID NO: NIS009722	CORE DRC APPROVAL DATE: 18JUL2024
EPIDEMIOLOGY NO.(PE STUDIES ONLY): EP08039.017	

Update no	Date	Section of Study Protocol	Update	Reason	CORE DRC Approval Date	CORE DRC Version No
4	23Nov23	7.8	Provided number of confirmed AoRRP cases in the Sweden registries and estimated power.	Estimated study power in Sweden alone is <80%.	18Jul24	4.0
5	12Feb24	6.12	Included additional study limitation	Acknowledge that younger birth cohorts have high herd protection.	18Jul24	4.0
6	05May24	All sections	Major amendment made to the protocol. Data from Denmark and Norway will be added to the study.	Insufficient power with data from Sweden alone. The protocol is now in harmony with the Juvenile RRP (JoRRP) protocol.	18Jul24	4.0
		1	Additional principal investigators added, sponsor information updated.	Due to combination of Sweden, Denmark, and Norway data.	18Jul24	4.0
		2	Amended the study population and updated sample size/power estimates.	Due to combination of Sweden, Denmark, and Norway data.	18Jul24	4.0
		4	Milestone dates updated.	Due to delay caused by the decision to combine Sweden, Denmark, and Norway data to attain	18Jul24	4.0

PRODUCT: V501/V503	PROTOCOL/AMENDMENT VERSION NO.: V503-088-01-v1
REVOPS ID NO: NIS009722	CORE DRC APPROVAL DATE: 18JUL2024
EPIDEMIOLOGY NO.(PE STUDIES ONLY): EP08039.017	

Update no	Date	Section of Study Protocol	Update	Reason adequate power for the analysis.	CORE DRC Approval Date	CORE DRC Version No
		5, 6, 7.1, 7.2, 7.7, 7.9, 7.10, Annex 1, Annex 2	Amended these sections to include information from Denmark and Norway.	Due to combination of Sweden, Denmark, and Norway data.	18Jul24	4.0
		7.1	Cohort: Added justification to use the age group 15-29 years for the AoRRP protocol. Added Table 1 and Figure 1 to describe the ages, birth cohorts, and calendar years of coverage of included participants from Sweden, Denmark, and Norway.	Clarification of ages, birth cohorts, and calendar years of coverage of included participants from Sweden, Denmark, and Norway.	18Jul24	4.0
		7.1	Cases: Updated this section to highlight different case definitions for Sweden, Denmark, and Norway for more accurately capturing AoRRP cases in those countries along with a justification for this approach.	Clarification and description of case definition.	18Jul24	4.0
		7.6.1	Added a clarification that a person will be classified as unexposed if they did not receive even a single dose of Gardasil prior to being selected as a case or control in the study.	To clarify exposure.	18Jul24	4.0

PRODUCT: V501/V503	PROTOCOL/AMENDMENT VERSION NO.: V503-088-01-v1
REVOPS ID NO: NIS009722	CORE DRC APPROVAL DATE: 18JUL2024
EPIDEMIOLOGY NO.(PE STUDIES ONLY): EP08039.017	

Update no	Date	Section of Study Protocol	Update	Reason	CORE DRC Approval Date	CORE DRC Version No
		7.6.2	Added use of topography/morphology or SNOMED/Norpat codes from pathology registries to define AoRRP cases.	To clarify outcome definition.	18Jul24	4.0
		7.8	Updated the power calculation, sample size estimates, and Table 2, which describes estimated power based on varying the effect size, vaccination coverage, and number of AoRRP cases. Provided a justification to pool data from Sweden, Norway, and Denmark.	Due to combination of Sweden, Denmark, and Norway data.	18Jul24	4.0

PRODUCT: V501/V503	PROTOCOL/AMENDMENT VERSION NO.: V503-088-01-v1
REVOPS ID NO: NIS009722	CORE DRC APPROVAL DATE: 18JUL2024
EPIDEMIOLOGY NO.(PE STUDIES ONLY): EP08039.017	

